BMI: Categorical variable. Obtained from EHR. Categories will be BMI of 24.9 or less, BMI 25-29.9, and BMI greater than or equal to 30.

Nicotine use: Dichotomous variable. Obtained from EHR. Current use at time of injury.

History of Diabetes: Dichotomous variable. Obtained from EHR.

ICD Code: Categorical Variable. Obtained from EHR.

Laterality: Categorical Variable. Left or Right TKA

Complications: Categorical Variable. Pulmonary embolism/deep vein thrombosis, surgical site infection, severe pain from the injections, other, and multiple for more than one complication.

10.3 At any point in the study, will you request, use, or access health information in any form, including verbal, hard copy and electronic?

Yes No

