Patients will be recruited through use of a HIPAA Waiver to access joint surgeon case lists. Patients scheduled for a TKA will be contacted by the principal investigator and informed of the study. Those who desire to participate will have study inclusion/exclusion criteria reviewed to determine eligibility. Those eligible will be scheduled a consent appointment. The investigator will offer to email (or provide by hard copy) consent document to review prior to the appointment. When patients return for consenting, they will be taken to a private room (clinic exam room or private room in the PACU) to conduct the consent procedures. Consent documents will be reviewed with patients and any questions asked will be answered. Patients who desire to enroll in the study will sign the consent documents. The investigator will sign the consent documents, then provide a copy to the patient. During the recruitment and consenting phase, the PI or AI will not be in military uniform or have their rank visible.

13.5 DoDI 3216.02 requires an ombudsman to be present during recruitment briefings when research involves greater than minimal risk and recruitment of Service members occurs in a group setting. If applicable, you may nominate an individual to serve as the ombudsman.

N/A
 Propose ombudsman

13.6 Withdrawal from Study Participation:

Explain the process for withdrawal and specify whether or not the subjects will be given the opportunity to withdraw their data or specimens in the event they wish to withdraw from the study

At any point in the study participants can self-withdrawal from the study if they have a poor response to the injections, are unable to tolerate all injections, not willing to complete questionnaires, intraoperative complications (pulmonary embolism, deep vein thrombosis, surgical site infection, multiple or other), not willing to bring in their medications or if they choose to no longer participate in the study. However, any data collected prior to withdrawal will still be analyzed.

14.0

Risks and Benefits

14.1

Risks of Harm:

Identify all research-related risks of harm to which the subject will be exposed for each research procedure or intervention as a result of participation in this study. Consider the risks of breach of confidentiality, psychological, legal, social, and economic risks as well as physical risks. Do not describe risks from standard care procedures; only describe risks from procedures done for research purposes

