Adverse events such as infection, damage to vascular structures that cause hematoma and excessive bleeding, injection of lidocaine into the blood stream are identified will be reported to the IRB. These adverse events will be monitored for during each visit through visually inspecting the injection sites and completing a neurovascular evaluation. The patient may also verbally inform the principal investigator of any of these potential adverse effects. The IRB will be notified by completing and submitting an eIRB Reportable Event Form (serious adverse event, unanticipated problem) or reporting at the time of continuing review (all others). The form will be routed to the DGMC C&T Board. The DGMC HRPP staff regularly monitor C&T Board notifications; they will notify the institution's HRPO of the reportable event by email, telephone, or in-person until it has been received and acknowledged. If any adverse event takes place the design of this study will be examined and determine if research protocol needs to be revised.

17.0**Equipment/non-FDA Regulated Devices**

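### Section 13.6 offers counted complications as reasons to withdraw but plans no safety capture afterwards, so an event's later course and any later event may go unrecorded

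*Combined protocol and SAP*

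**What the plan says.** Section 13.6 describes withdrawal as the participant's own choice: "At any point in the study participants can self-withdrawal from the study if they have a poor response to the injections, are unable to tolerate" the full set of injections. The list continues with unwillingness to complete questionnaires, "intraoperative complications (pulmonary embolism, deep vein thrombosis, surgical site infection, multiple or other", unwillingness to bring in medication, and finally simply no longer wishing to take part. It closes: "However, any data collected prior to withdrawal will still be analyzed". It says nothing about data after withdrawal.

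Section 10.2 defines a Complications variable with these codes: "Pulmonary embolism/deep vein thrombosis, surgical site infection, severe pain from the injections, other, and multiple for more than one complication". It attaches no time limit to them.

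Section 16.1 states how adverse events are found: "These adverse events will be monitored for during each visit through visually inspecting the injection sites and completing a neurovascular evaluation". It adds a second route: "The patient may also verbally inform the principal investigator of any of these potential adverse effects".

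Section 10.1, Step 4 has the investigator read complications from MHS Genesis on POD0. Step 5 returns to the record on POD1 for opioid totals, not for complications. Steps 5 to 7 place the remaining contacts at POD1, week 2 and week 6, with a reminder call before each of the last two visits.

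**The concern.** The reasons 13.6 offers for leaving are largely the safety outcomes the trial intends to count. Leaving can therefore be related to harm, and the people most likely to leave for these reasons are those whose follow-up tells most about safety. The study injections are given in one session on POD0, so a participant who leaves later stops no further study treatment. What ends is the questionnaires, the pill counts and the scheduled safety checks.

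At stake are whether an event resolved and whether another followed, such as a later thrombosis or infection. This is separate from how missing VAS scores are handled: pairwise deletion in 11.1 concerns the analysis of values and does not create a safety observation that nobody was asked to make.

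**Working it through.** The plan states no figure for this point, so the check sets the sections side by side.

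**1. Do the exit reasons match the counted events?**

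| Code in 10.2 | Named in 13.6? |
|---|---|
| Pulmonary embolism / deep vein thrombosis | Yes, as two items |
| Surgical site infection | Yes |
| Other | Yes |
| Multiple | Yes |
| Severe injection pain | Not by name; nearest are poor response and inability to tolerate all injections |

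Four of five codes match directly, and the fifth plausibly overlaps with two further exit reasons.

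**2. What capture is scheduled, and for whom?**

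| Route | Participant who stays | Participant who withdraws after an event |
|---|---|---|
| Record review for complications, POD0 (Step 4) | Yes | Yes, but it covers POD0 only |
| Site inspection and neurovascular check at visits (16.1) | Yes | Up to withdrawal; none described after |
| Record review for complications after POD0 | None described | None described |
| Verbal report to the principal investigator (16.1) | Open | Not ruled out, but depends on someone who has left |

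A review on the day of surgery cannot show what happens later. Once visits stop, the last row is the only route left, and nobody is scheduled to ask.

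**3. What is kept?** An event that prompts withdrawal comes before it. If it was recorded by then, 13.6 keeps it. At risk are its later course and any subsequent event.

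**4. Does the word intraoperative fit?** The injections follow the TKA on POD0 (9.2; 10.1, Steps 3a and 3b), so a truly intraoperative event precedes them. Section 10.2 counts the same events without that limit, alongside severe injection pain, which can arise only from the injections. Surgical site infection also sits poorly under that label. The two sections need reconciling.

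**5. Can the loss be sized?** Section 11.5 allows up to 5 of 15 per group to drop out: 5/15 = 33% (the plan writes 30%), leaving 15 - 5 = 10. That allowance serves the VAS power calculation and covers every cause, so it does not measure safety loss.

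For context only, the one-sided 95% upper limit on an event rate when zero events are seen in n people is 1 - 0.05^(1/n):

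- n = 10: 1 - 0.05^(1/10) = 26%
- n = 15: 1 - 0.05^(1/15) = 18%
- n = 50 (the maximum per group in 11.2): 1 - 0.05^(1/50) = 6%

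These limits show that, at the planned 10 to 15 per group, a single unrecorded event would change the safety description. They do not estimate how many events would be missed.

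**The case against.** The strongest reply is that 13.6 takes nothing away. Withdrawal is voluntary and open for any reason, so no harmed participant is made to leave, and those who stay keep their week 2 and week 6 visits. Deleting complications from the list would change little, because the same person could leave under the final clause. This stands, and it is why the remedy below does not rest on editing the list.

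Second, a reader might infer that only pre-withdrawal data are kept and that safety follow-up stops. The documents say neither. The sentence on earlier data is a statement that those data are retained; it does not discard or forbid later data. The gap is one of silence.

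Third, it would be wrong to say that adverse events are found only at visits, since 16.1 also provides for verbal report. That route is real but passive.

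Fourth, an enrolled participant could have an event during surgery and leave before being injected, which gives the word intraoperative a coherent meaning. That explains one case, but not the fit with surgical site infection or with 10.2.

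Fifth, the consent form was not available for this review, and the choice of monitoring arrangement in 15.1 cannot be read in this copy. Either might address follow-up after withdrawal. The point is therefore limited to the visible text.

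**Conclusion.** The point holds as a gap in the visible plan. For a participant who withdraws after a complication, no capture of its later course or of later events is scheduled; only voluntary verbal report remains. The word intraoperative in 13.6 is also inconsistent with the unrestricted complications in 10.2.

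The documents do not support the reading that harmed participants must leave, that their later data are discarded, or that a third of an arm would lose safety follow-up. The last would require every dropout in the 11.5 allowance to have left because of harm, and nothing in the plan links the two.

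The size of the loss is unknown. It depends on how many participants have an event, how many of those leave, and whether the consent form already provides for follow-up. This is a low-cost improvement to safety reporting and does not affect the validity of the VAS comparison. It needs settling before participants consent, because permission for later record review and observations never collected cannot be supplied at the analysis stage.

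**What to change.** - In 13.6 and the consent form, separate two decisions: stopping study procedures, and withdrawing permission for safety follow-up.
- For anyone who received a study injection and does not withdraw that permission, continue complication capture to week 6, by visit or, if visits stop, by MHS Genesis review. MHS Genesis is already a study data source.
- Record the reason for each withdrawal, so that departures after an event can be reported by group.
- Reconcile the word intraoperative in 13.6 with the complications in 10.2, which carry no such limit.

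The cost is wording in two documents, a few extra chart reviews, and asking participants who leave whether record review may continue. The right to leave for any reason is unchanged.

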17.1 Does the study involve the use of any unique non-medical devices/equipment?

Yes No

18.0**FDA-Regulated Products****18.1 Will any drugs, dietary supplements, biologics, or devices be utilized in this study?**

- Drugs
- Dietary Supplements
- Biologics
- Devices
- N/A

18.2 Drugs, Dietary Supplements and Biologics/Vaccines details:

- Are drug(s) in this research being used in accordance to the approved labeling?
- Are drug(s) in this research being used in a manner other than its approved labeling?

Enter Dietary Supplements and Biologics/Vaccines in the Drug Information table. Complete all relevant fields in the table ("Protocol Drug Details" screen). If the question is not relevant, leave the question blank and/or do not change the default selection.

View Details	Drug Name	FDA Approved	A new drug or a new use of an already approved drug:	IND Number
⊖	Trade Drug Name: lidocaine 1-2% with or without epinephrine Generic Drug Name: Investigational Drug Name:	Yes	No	

Trade Drug Name:	lidocaine 1-2% with or without epinephrine
Generic Drug Name:	
Investigational Drug Name:	
Identify the name of the manufacturer or source of investigational drug/biologic:	Hospira
Is the drug supplied at no cost?	Yes
Is the Drug FDA Approved:	Yes
Is this a new drug or a new use of an already approved drug	No
Is an IND necessary	No
IND Number	
Who holds the IND:	N/A
IND details:	
If FDA Approved and an IND is	

not required, Please provide a rationale for exemption:	
Are you currently using this IND in another research project?	No
If yes, list the IRB Number(s):	
Dose Range:	4mL
Frequency:	once
Route of administration:	intramuscular
Will the investigational pharmacy be dispensing?	Yes
If the source is not a FDA licensed facility, provide details regarding the purity, quality, stability and sterility of the investigational drug/biologic:	
Identify who will be preparing the investigational drug /biologic for administration and describe in detail how it will be prepared:	The PI will remove the lidocaine 1% without epinephrine from the pyxis within the orthopedics clinic. Once the medical is removed the PI will wear gloves and prepare 4 25-gauge needles and 4 5 mL syringes. Once all needles are attached to the syringes the cover to the lidocaine will be removed and cleaned with alcohol swabs before each draw. Once 1 mL of lidocaine 1% without epinephrine is prepared in each syringe the needles will be recapped and immediately go to the patient's room for injection.
Indication(s) under Investigation:	
Where will the drug be stored	Orthopedic clinic pyxis
Drug Storage Restrictions (including temperature, etc.):	Medication will be stored in the clinic pyxis at room temperature
Administration Instructions:	Prior to injection the PI will identify those anatomic landmarks meant for injection. Then the areas will be marked by indenting the skin with an empty pen, there will not be any ink on the injection site. The area will be prepped with chlorohexidine. Once the site is prepped the investigator will make two injections into the muscle belly and injection 0.5mL of lidocaine 1% without epinephrine. Once the needle is removed it will be discarded in the appropriate sharp's container. The area will then be cleaned with alcohol swabs and a band aid applied. These steps will be repeated for all 4-injection sites.
Possible Untoward Effects, Their Symptoms & Treatment:	
Potential or Actual Antidotes for Excessive or Adverse Drug Effect:	
Contraindications and Interactions, If Known:	Allergy to medication
Investigators Authorized to Prescribe:	PI and AI are authorized to prescribe lidocaine 1% without epinephrine

18.4 Reporting Requirements for FDA-regulated research under IND and IDE:

Describe the process for complying with FDA regulatory requirements for adverse event reporting and adverse device effects reporting to the sponsor

N/A

18.5 Sponsor (organization/institution/company):

N/A

If applicable, provide sponsor contact information:

19.0 Research Registration Requirements

19.1 ClinicalTrials.gov Registration:

- Registration is not required
- Registration pending
- Registration complete

19.2 Defense Technical Information Center Registration (Optional):

- Registration is not required
- Registration pending
- Registration complete

